2.4.3 Toxicology

The toxicity of [¹²⁴I]*mIBG* can be split into two components; that arising from the administered chemical dose of *mIBG* and that arising from the radioactive dose of iodine-124. The former component has been characterised preclinically in studies of *mIBG* toxicity, however, this has largely been superseded by extensive clinical use of radiolabelled *mIBG* both as a diagnostic radiopharmaceutical and as a targeted radiotherapeutic. The dosimetry of [¹²⁴I]*mIBG* has been calculated with reference to published biokinetic data (see Section 2.5.4).

In rats administration of intravenous *mIBG* at 20 to 40 mg/kg/day (120 to 240 mg/m²/day) induces signs of serious toxicity with 20 mg/kg considered to be the maximum tolerated dose. At doses of 5 to

CONFIDENTIAL

20 mg/kg/day (30 to 120 mg/m²) some acute effects were observed, including respiratory distress, but the only long-term effects documented were a slight increase in weight of the liver and heart.

In dogs intravenous administration of *m*IBG at 20 mg/kg/day (400 mg/m²/day) was a lethal dose. Lower dose levels (14 mg/kg, 280 mg/m²) produced transient toxic cardiac effects. Repeated intravenous administration of *m*IBG to dogs at 2.5 to 10 mg/kg (50 to 200 mg/m²) was also found to induce some cardiovascular effects, including increased blood pressure, increases in heart rate and in cardiac pulse propagation, but all signs were of a transient nature (Smets, Bout et al. 1988, GE Healthcare Limited 2009).

The [¹²⁴I]*m*IBG prepared for this study will have a maximum possible administered chemical dose of 10 µg per patient. This chemical dose will be well within the range of human exposure to *m*IBG and is likely to be lower than that administered during the [¹²³I]*m*IBG scan the patient will have received prior to inclusion in this study. As a consequence the safety of *m*IBG can be directly inferred from the extensive and current routine use of [¹²³I]*m*IBG and [¹³¹I]*m*IBG in clinical practice.

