2.5.2 Pharmacokinetics and Metabolism

The pharmacokinetics of *m*IBG labelled with iodine-124 are expected to be identical to *m*IBG labelled with iodine-123 or iodine-131, i.e. rapid initial uptake in liver, lungs, myocardium, spleen and salivary glands (GE Healthcare Limited 2009).

After administration of *m*IBG, uptake of radioactivity generally reflects organs and tissues of either rich adrenergic innervation or with a role in catecholamine excretion. High levels of uptake are observed in the liver with lower levels observed in the spleen, lungs, salivary glands, skeletal muscle and myocardium. Myocardial uptake may be particularly high, especially in children under 1 year old (although patients under 1 year old will be excluded from this study). Radioactivity may accumulate to a variable degree in nasal mucosa, lungs, gallbladder, colon and uterus. No skeletal uptake is observed. Uptake in the thyroid was only observed when pre-treatment with non-radioactive iodide to competitively block the thyroid had been omitted. Distribution in patients and healthy subjects was comparable (Nakajo, Shapiro et al. 1983, Shapiro, Copp et al. 1985, Wafelman, Hoefnagel et al. 1994, Shulkin and Shapiro 1998, Bombardieri, Giammarile et al. 2010).

Data has been published on the pharmacokinetics of radioactivity after both diagnostic and radiotherapeutic [¹³¹I]*m*IBG administration. After intravenous administration of radiolabelled *m*IBG, radioactivity is distributed from the vascular compartment within one hour followed by a slow redistribution from the peripheral compartment into the central compartment. Terminal elimination half-life of radioactivity from blood has been reported to be 9 to 130 h in neuroblastoma patients (Wafelman, Hoefnagel et al. 1994, Vallabhajosula and Nikolopoulou 2011).

The excretion of radioactivity after administration of radiolabelled *m*IBG has been established clinically and the subject of published reviews (Shapiro and Gross 1987, Wafelman, Hoefnagel et al. 1994, Vallabhajosula and Nikolopoulou 2011). Following intravenous administration of radiolabelled *m*IBG radioactivity is rapidly and almost entirely excreted in urine. The importance of renal excretion is confirmed by faecal recoveries of radioactivity of less than 2%. As might be expected glomerular filtration rate (GFR) has a major influence with higher plasma/blood cell distribution ratios observed in renally impaired patients.

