7.4 EVALUATIONS DURING THE STUDY (DAY -7 TO DAY 1)

- Menarchal female patients should have a serum or urine human chorionic gonadotrophin (HCG) test; a negative result is required before administration of [¹²⁴I]mIBG
- Temperature, blood pressure (BP) and pulse rate
- Blood sample for full blood count and biochemistry (refer to criteria in Section 4.1.3 for required values) to include:
 - Haematology – haemoglobin, white blood cells (WBC) with differential count (absolute neutrophil count (ANC) and lymphocytes) and platelets
 - Biochemistry – serum bilirubin, alanine aminotransferase (ALT) and/or aspartate amino-transferase (AST) and/or alkaline phosphatase (ALP), creatinine
- *PLEASE NOTE: All evaluations required during the study between Day -7 and Day 1 must be completed and all results received prior to administration of [¹²⁴I]mIBG.*

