7.6 EVALUATIONS DURING THE STUDY (NOVEL IMAGING)

Following [¹²³I]mIBG planar scintigraphy ± SPECT for routine clinical care of neuroblastoma, patients will only continue in the study and undergo [¹²⁴I]mIBG imaging if they fulfil the additional clinical criteria outlined in Section 4.1.3.

7.6.1 [¹²⁴I]mIBG PET/CT scan

Day -1 Thyroid blockade

All patients will receive thyroid blockade (i.e. potassium iodide) for five consecutive days, starting the day before administration of [¹²⁴I]mIBG solution injection, i.e. one dose of potassium iodide taken on the day before the administration of [¹²⁴I]mIBG solution and 4 once daily doses of potassium iodide following the administration of [¹²⁴I]mIBG solution for a total of 4 days (please see section 7.9 Schedule of Events). Apart from the duration of dosing (i.e. the total number of days), the thyroid blockade administration should be administered according to the standard local practice for [¹³¹I]mIBG therapy.

Day 1 [¹²⁴I]mIBG administration

A minimum interval of 72 hours is required between injection of [¹²³I]mIBG and the [¹²⁴I]mIBG PET/CT scan to ensure scan quality. See Sections 5.2 and 6.3 for guidance on dose and administration.

Day 2 [¹²⁴I]mIBG PET/CT scan

To be performed **24 h (± 3 h) post-administration of [¹²⁴I]mIBG**. The patient's temperature, BP and pulse should be measured and an assessment of AEs and concomitant medications made during this visit to assess the safety of the [¹²⁴I]mIBG tracer administered on the previous day. If the scan schedule is likely to exceed 75 minutes as described in the study Information sheets and consent or assent forms then this should be discussed with the patient prior to the injection of [¹²⁴I]mIBG to seek verbal consent. Any discussions should be documented in the patients' medical notes.

7.6.2 [REDACTED]

[REDACTED]

- [REDACTED]
- [REDACTED]
- [REDACTED]

[REDACTED]

7.6.3 [REDACTED]

[REDACTED]

7.7 'OFF-STUDY' ASSESSMENT (DAY 3 TO DAY 7)

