7.9 SCHEDULE OF EVENTS

Observation/Investigation	Screening	During the study						Off-study
	Day -28 to enrolment	Day -21 to -3 ^e	Day -7 to 1 ^f	Day 1	Day 2	Day 3	Day 4	Day 3-7 ^m
Written informed consent ^a	X							
Inclusion and exclusion criteria	X							
Demographics	X							
Medical history ^b	X							
Routine imaging: conventional cross sectional CT/MRI ^c	X							
Adverse event evaluation ^d		Continuously monitored from time of consent until Off-study						
Concomitant treatments		Continuously monitored from time of consent until Off-study						
Physical examination	X							
Height and weight	X							
WHO or Lansky performance status	X							
Enrolment on the study	X							
[¹²³ I]mIBG administration ^e		X						
[¹²³ I]mIBG planar scintigraphy ± 3D imaging by SPECT ^e		X						
Serum or urine pregnancy test ^g			X ^f					
Temperature, blood pressure, pulse			X ^f		X			
Full blood count and biochemistry ^h			X ^f					
Thyroid blockade ⁱ			X	X	X	X	X	
[¹²⁴ I]mIBG administration				X				
[¹²⁴ I]mIBG PET/CT scan ^j					X			

CONFIDENTIAL

Footnotes:

- a **Informed consent** from the patient's parent or guardian is required for all patients under 16 years of age. Written or verbal assent will be sought from all patients under 16 years of age. Informed consent is required from all patients aged 16 or above.
- b Relevant **medical history** including prior diagnosis, genetic findings to include *MYCN*, 11q, 17q and other segmental chromosomal abnormalities of prognostic impact in neuroblastoma, histological findings according to The International Neuroblastoma Pathology Classification (the Shimada system), prior treatment for neuroblastoma (stage 4 disease only) and concomitant diseases.
- c Routine **imaging** for assessment of neuroblastoma including conventional cross sectional CT and/or MRI as clinically indicated. This routine imaging must be performed during a break in treatment and within the 28 days before administration of [¹²⁴I]mIBG.

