- d **Adverse events (AEs)**, including serious adverse events (SAEs), must be monitored from the time the patient consents/assents to any protocol-specific procedure. The Investigator should determine the start and stop date of an AE together with the relationship of the event to [¹²⁴I]mIBG. All AEs must be graded according to NCI CTCAE Version 4.02. All AEs and any concomitant treatment must be recorded in the medical records and in the eCRF. (See Section 8.3 for further details regarding the definition of AEs and reporting requirements.)
- e [¹²³I]mIBG **planar scintigraphy ± SPECT** should be performed following an interval of at least 7 days from previous anti-cancer therapy. A minimum interval of 72 hours is required between injection of [¹²³I]mIBG tracer and the [¹²⁴I]mIBG PET/CT scan. Thyroid blockade should be given according to local practice for administration of [¹²³I]mIBG.
- f Day -7 to 1 assessments should only be performed after the results of [¹²³I]mIBG planar scintigraphy confirm the presence of at least 1 lesion.
- g Menarchal females should have a serum or urine HCG test to rule out **pregnancy**. A negative result must be obtained before the administration of [¹²⁴I]mIBG.
- h **Full blood count** to include haemoglobin, WBC with differential count (ANC and lymphocytes) and platelets, and biochemistry to include serum bilirubin, ALT or AST or ALP, creatinine). Refer to Section 4.1.3 Clinical Criteria for [¹²⁴I]mIBG imaging for required values.
- i For administration of [¹²³I]mIBG **thyroid blockade** should be given according to local practice. For administration of [¹²⁴I]mIBG, potassium iodide should be given for five consecutive days, starting the day before [¹²⁴I]mIBG administration, according to local practice for administration of [¹³¹I]mIBG.
- j [¹²⁴I]mIBG **PET/CT scan** to be performed 24 h (± 3 h) after the administration of [¹²⁴I]mIBG. A minimum interval of 72 hours is required between injection of [¹²³I]mIBG tracer and the [¹²⁴I]mIBG PET/CT scan. The Investigator must ensure patients meet the Clinical Criteria for [¹²⁴I]mIBG imaging described in section 4.1.3 before administration of [¹²⁴I]mIBG Solution for Injection.
- k [REDACTED]
- l [REDACTED]

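### The two scheduled sets of vital signs cannot show a brief, symptomless change around the [¹²⁴I]mIBG infusion, and the baseline set may be a week old at dosing

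*Combined protocol and SAP*

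**What the plan says.** **Readings after dosing.** Protocol section 7.6.1 places the PET/CT scan at "24 h (± 3 h) post-administration of [¹²⁴I]mIBG". At that visit "temperature, BP and pulse should be measured and an assessment of AEs and concomitant medications made during this visit to assess the safety" of the tracer. The vital signs therefore have a stated safety purpose.

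**Readings before dosing.** Section 7.4 lists temperature, blood pressure and pulse in the Day -7 to Day 1 block and adds: "All evaluations required during the study between Day -7 and Day 1 must be completed and all results received prior to administration". Footnote f to section 7.9 delays the start of that block: "Day -7 to 1 assessments should only be performed after the results of [¹²³I]mIBG planar scintigraphy confirm the presence of at least 1 lesion".

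**The schedule.** In section 7.9 the row "Temperature, blood pressure, pulse" is marked under Day -7 to 1 and under Day 2. The Day 1 column is empty in that row. Section 6.5 requires a slow infusion with recorded start and end times, but asks for no vital signs.

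**Adverse events.** The adverse event row of the same table reads "Continuously monitored from time of consent until Off-study".

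**Background.** Section 2.4.3 reports cardiovascular findings in dogs, "including increased blood pressure, increases in heart rate and in cardiac pulse propagation, but all signs were of a transient nature". Section 2.5.2 says that after injection "radioactivity is distributed from the vascular compartment within one hour". The same sentence goes on to a slow return from the peripheral compartment, and the section gives a terminal half-life in blood of 9 to 130 h.

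**The concern.** Safety of a single injection is a secondary objective (section 3.1). The introduction describes only two earlier recipients of the ¹²⁴I-labelled compound, and section 4.1.3 itself points to limited experience with it. The acute effects in the protocol's own background are short-lived ones: blood pressure and heart rate changes in dogs, and dizziness or flushing after [¹²³I]mIBG. One would expect the objective measurements to bracket the infusion. Instead, one set comes about a day later and the other may come a week before.

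Two problems follow. A normal Day 2 set could be read as evidence of haemodynamic safety during the infusion, which it does not address. An abnormal Day 2 set, compared with an old baseline, could reflect the underlying illness rather than the tracer. Section 4.1.3 admits patients aged 16 or under with neutrophils down to 0.2 × 10⁹/L and haemoglobin down to 7.0 g/dl, with transfusion and G-CSF allowed, so temperature and pulse may move for other reasons. Every related category in section 8.3.3 requires an onset that fits the time of administration, and these two readings may not supply it.

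**Working it through.** No sample size or error rate is involved. The check is of timing, followed by two side calculations that limit how far the point can go.

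1. **Time from injection to the Day 2 reading** (7.6.1). 24 − 3 = 21 h and 24 + 3 = 27 h. The earliest reading is 21 − 1 = 20 h after the end of the one-hour vascular phase in 2.5.2.

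2. **Age of the baseline** (7.4, 7.9). Section 7.6.1 calls the day before administration Day -1, so there is no Day 0.
   - Taken on Day 1: 0 days old at dosing, 1 day by Day 2.
   - Taken on Day -7: 6 days to Day -1 plus 1 to Day 1 = 7 days old at dosing, 8 by Day 2.
   - Footnote f narrows this for late scans. If the planar scan is on Day -3, the baseline cannot precede it: 2 days to Day -1 plus 1 = at most 3 days at dosing, 4 by Day 2. The 7-day figure needs a planar result by Day -7, which the Day -21 to -3 scan window permits.

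3. **What each source can record.**

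| Event after the infusion | Scheduled vital signs | Adverse event reporting |
|---|---|---|
| Brief change, no symptoms, not measured | Not recorded | Not recorded |
| Brief reaction, felt or observed | Not recorded | Recorded |
| Change still present at 21 to 27 h | Recorded, but onset uncertain if the baseline is old | Recorded if judged an adverse event |

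   Section 8.3.1 allows a physiological observation to count as an adverse event, but someone has to make the observation. The first row is the gap.

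4. **Does the one-hour figure make the Day 2 reading empty?** Take first-order decline in the terminal phase, fraction left = 0.5^(t / half-life), at t = 24 h.
   - Half-life 9 h: 0.5^(24/9) = 0.16.
   - Half-life 130 h: 0.5^(24/130) = 0.88.

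   So 16% to 88% of the terminal-phase blood level remains. One hour describes the vascular phase only. These figures concern radioactivity and say nothing direct about how long a blood pressure effect lasts.

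5. **Dose margin.** The lowest repeated dog dose with cardiovascular signs is 2.5 mg/kg = 2,500 µg/kg (2.4.3). Margin = 2,500 / (10 µg / weight), using Table 2 weights and the 3 kg floor in 4.1.3.
   - 73.7 kg: 10/73.7 = 0.136 µg/kg, margin 18,425.
   - 9.72 kg: 10/9.72 = 1.03 µg/kg, margin 2,430.
   - 3 kg: 10/3 = 3.33 µg/kg, margin 750.

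   Section 2.5.3 gives a maximum chemical dose of 50 µg, while 1.3, 2.4.1, 2.4.3 and 5.3 give 10 µg. The 200-fold figure in 2.5.3 reproduces with 50 µg (10,000/50 = 200); with 10 µg it would be 10,000/10 = 1,000. At 50 µg the margins above fall five-fold, to 3,685, 486 and 150. The passages must be reconciled.

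**The case against.** The strongest reply is that the safety objective does not depend on vital signs. Its endpoint is the causality and CTCAE grade of adverse events (3.1; SAP 1.2), tabulated by frequency, grade and relationship (12.2.4; SAP 3.1.5). Adverse events are followed continuously, and the Day 2 visit includes an adverse event assessment. The [¹²³I]mIBG study that section 2.5.3 treats as most relevant also observed patients over 24 h. This stands. A reader might infer that acute effects cannot be seen at all. The documents do not support that: flushing, dizziness or any other reaction felt or noticed would be reported. What remains outside is a change that is both brief and silent. Patients are eligible from age 1, when self-report of symptoms is limited.

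A reader might also infer from the one-hour statement that distribution is over long before Day 2. The rest of the sentence and the half-life rule that out.

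Section 2.4.1 expects no significant pharmacodynamic effect at this dose, section 2.5.3 calls such effects very rare with slow injection, and section 6.5 requires slow infusion. Section 2.4.3 adds that the safety of the compound can be inferred from its routine use with other iodine isotopes. All of this makes an effect unlikely and keeps the point minor. It does not make a 24 h reading informative about the infusion.

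Finally, a reader might infer that no patient has an early post-dose reading. That cannot be asserted. Sections 7.6.2 and 7.6.3 and footnotes k and l are redacted, and section 2.5.4 mentions 4 h scans in up to six patients.

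**Conclusion.** The point holds as a low-priority improvement to data collection. In the visible main-study schedule, the only required post-dose vital signs fall 21 to 27 h after injection, and the baseline may be 0 to 7 days old at dosing. These readings cannot detect a transient, symptomless change around the infusion. With an old baseline, a Day 2 change cannot be timed to the tracer. Acute safety therefore rests on adverse event reporting, and a normal Day 2 set should not be cited as evidence about the infusion period.

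This rests on three assumptions: there is no Day 0 (with one, the upper limits would be 8 days at dosing and 9 by Day 2); no local practice adds readings that enter the trial data; and the redacted sub-study text, whatever it contains, does not cover all patients. The primary endpoint, the two-stage design and the stopping decisions are untouched.

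**What to change.** In sections 7.4 and 7.9, specify that the baseline temperature, blood pressure and pulse already required be recorded on Day 1 immediately before the infusion. This stays inside the existing window and leaves the blood tests and pregnancy test where they are. In 12.2.4 and SAP 3.1.5, add a descriptive summary of paired Day 1 to Day 2 changes.

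Optionally, record one further set as data collection after the infusion ends while the patient is on site. If this is not done, state in the clinical study report that the scheduled vital signs do not address the infusion period.

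The cost is a few minutes on Day 1, one eCRF field (with a schedule line for the optional set), and loss of the freedom to take the baseline earlier with the blood tests. No dose, treatment or clinical management rule changes.

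The SAP addendum follows a review of the statistical report in November 2020. If scanning is already complete, only the reporting statement applies here, and the schedule change belongs in the larger studies foreseen in section 2.6.

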7.8 FOLLOW-UP

AEs considered to have a highly probable, probable or possible causal relationship to [¹²³I]mIBG and/or [¹²⁴I]mIBG present at the time of the Off-Study assessment should be followed until resolution, recovery to baseline, or stabilisation of these events, unless the patient starts another anti-cancer therapy.

CONFIDENTIAL

7.9 SCHEDULE OF EVENTS

Observation/Investigation	Screening	During the study						Off-study
	Day -28 to enrolment	Day -21 to -3 ^e	Day -7 to 1 ^f	Day 1	Day 2	Day 3	Day 4	Day 3-7 ^m
Written informed consent ^a	X							
Inclusion and exclusion criteria	X							
Demographics	X							
Medical history ^b	X							
Routine imaging: conventional cross sectional CT/MRI ^c	X							
Adverse event evaluation ^d		Continuously monitored from time of consent until Off-study						
Concomitant treatments		Continuously monitored from time of consent until Off-study						
Physical examination	X							
Height and weight	X							
WHO or Lansky performance status	X							
Enrolment on the study	X							
[¹²³ I]mIBG administration ^e		X						
[¹²³ I]mIBG planar scintigraphy ± 3D imaging by SPECT ^e		X						
Serum or urine pregnancy test ^g			X ^f					
Temperature, blood pressure, pulse			X ^f		X			
Full blood count and biochemistry ^h			X ^f					
Thyroid blockade ⁱ			X	X	X	X	X	
[¹²⁴ I]mIBG administration				X				
[¹²⁴ I]mIBG PET/CT scan ^j					X			

CONFIDENTIAL

Footnotes:

- a **Informed consent** from the patient's parent or guardian is required for all patients under 16 years of age. Written or verbal assent will be sought from all patients under 16 years of age. Informed consent is required from all patients aged 16 or above.
- b Relevant **medical history** including prior diagnosis, genetic findings to include *MYCN*, 11q, 17q and other segmental chromosomal abnormalities of prognostic impact in neuroblastoma, histological findings according to The International Neuroblastoma Pathology Classification (the Shimada system), prior treatment for neuroblastoma (stage 4 disease only) and concomitant diseases.
- c Routine **imaging** for assessment of neuroblastoma including conventional cross sectional CT and/or MRI as clinically indicated. This routine imaging must be performed during a break in treatment and within the 28 days before administration of [¹²⁴I]mIBG.
- d **Adverse events (AEs)**, including serious adverse events (SAEs), must be monitored from the time the patient consents/assents to any protocol-specific procedure. The Investigator should determine the start and stop date of an AE together with the relationship of the event to [¹²⁴I]mIBG. All AEs must be graded according to NCI CTCAE Version 4.02. All AEs and any concomitant treatment must be recorded in the medical records and in the eCRF. (See Section 8.3 for further details regarding the definition of AEs and reporting requirements.)
- e [¹²³I]mIBG **planar scintigraphy ± SPECT** should be performed following an interval of at least 7 days from previous anti-cancer therapy. A minimum interval of 72 hours is required between injection of [¹²³I]mIBG tracer and the [¹²⁴I]mIBG PET/CT scan. Thyroid blockade should be given according to local practice for administration of [¹²³I]mIBG.
- f Day -7 to 1 assessments should only be performed after the results of [¹²³I]mIBG planar scintigraphy confirm the presence of at least 1 lesion.
- g Menarchal females should have a serum or urine HCG test to rule out **pregnancy**. A negative result must be obtained before the administration of [¹²⁴I]mIBG.
- h **Full blood count** to include haemoglobin, WBC with differential count (ANC and lymphocytes) and platelets, and biochemistry to include serum bilirubin, ALT or AST or ALP, creatinine). Refer to Section 4.1.3 Clinical Criteria for [¹²⁴I]mIBG imaging for required values.
- i For administration of [¹²³I]mIBG **thyroid blockade** should be given according to local practice. For administration of [¹²⁴I]mIBG, potassium iodide should be given for five consecutive days, starting the day before [¹²⁴I]mIBG administration, according to local practice for administration of [¹³¹I]mIBG.
- j [¹²⁴I]mIBG **PET/CT scan** to be performed 24 h (± 3 h) after the administration of [¹²⁴I]mIBG. A minimum interval of 72 hours is required between injection of [¹²³I]mIBG tracer and the [¹²⁴I]mIBG PET/CT scan. The Investigator must ensure patients meet the Clinical Criteria for [¹²⁴I]mIBG imaging described in section 4.1.3 before administration of [¹²⁴I]mIBG Solution for Injection.
- k [REDACTED]
- l [REDACTED]
- m The Investigator should make an assessment of AEs and record concomitant medications either during a routine visit to the clinic or by telephone between Day 3 to Day 7. Patients should not receive any anti-cancer therapy or investigational drugs until after this Off-Study Assessment. AEs considered to have a highly probable, probable or possible causal relationship to [¹²⁴I]mIBG still present at the Off-study assessment should be followed until resolution, recovery to baseline, or stabilisation of these events, unless the patient starts another anti-cancer therapy.

